Additional comparisons across treatment periods for subjects receiving Omegaven® will be aimed to assess occurrence of spontaneous bleeding (e.g., unexplained bruising, oozing from gums/incision sites), and maximum triene/tetraene ratio, minimum platelets, and maximum international normalized ratio (INR), trends in pre-albumin (age standardized levels). We will also explore trends in coagulopathies based on curves of platelets, prothrombin time (PT), partial thromboplastin time (PTT) over time, and INR. We will also describe the rate with which INR ratios were > 2 (number of days/follow-up time), as a marker of coagulopathies.

Additional comparisons between Omegaven® and soybean oil fat emulsion groups will be performed with regards to rate in which albumin is > 3 g/dL, maximum triglyceride level, rate of blood stream infections (number of positive blood cultures/follow-up-time under PN after baseline), rate of central venous catheter (CVC) infections (number of CVC infections/follow-up time and number of gram positive CVC infections/follow-up time), and occurrence of anaphylactic reactions after baseline.

Nutritional outcomes between Omegaven® and soybean oil fat emulsion groups that will be compared include changes in weight- and height-for-age Z-scores from baseline to 10% PN or cessation of PN..

We will describe trends over time for all outcomes associated with fatty acid profiles (including triene/tetraene ratios, triglycerides, total omega-6 fatty acids, total omega-3 fatty acids, total saturated, total monounsaturated, and total polysaturated fatty acids). Specific fatty acids such as arachidonic, palmoleic, palmitic, oleic, stearic, and linoleic fatty acids will also be evaluated and described. Also, for exploratory purposes, we will compare the trend in weight- and height-for-age Z-scores between both groups.

2. Omegaven®

3. The patient will complete treatment with Omegaven® in this study when he/she is completely off PN, develops a contraindication for further use, or the patient/family requests to be removed from the study.

f. Data Collection Methods, Assessments and Schedule

Omega-3 Fat Emulsion (Omegaven™)

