We will also compare nutritional outcomes of the two groups including difference in weight-for- age Z-scores and height-for-age Z-scores from baseline to the moment in which the child starts enteral feeding and to the moment in which the child receives less than 10% of their calories from PN. Comparison between study groups will be performed via t-test or Wilcoxon tests, as appropriate. Using linear regression, we will explore adjustment for baseline alternative predictors of interest. Trends over time in Z-scores will also be explored using regression with repeated measure methods.

Analysis of Efficacy of Omegaven®

The primary outcome to gain preliminary evidence of efficacy will be based on the time from baseline to normalization of bilirubin level, i.e, first time point among three consecutive in which bilirubin is < 2 mg/dL. We do not anticipate that any subject will present a rebound on direct bilirubin after normalization. However, we will describe the cohort with respect to the frequency of rebounds in bilirubin levels.

Crude comparisons of time to normalize direct bilirubin levels between Omegaven® and soybean oil fat emulsion patients will be based on Kaplan-Meier curves and log-rank tests. We will estimate hazard ratios and adjust for potential baseline confounders using Cox-proportional hazard models. For all survival analysis based on non-parametric or semi-parametric methods, we will attribute an infinite time to event (i.e., time to event larger than the largest follow-up time in the whole study population) for subjects who die or receive a liver transplant before bilirubin is normalized. Subjects who die before their bilirubin levels normalize (particularly due to liver failure) have in fact the worse outcome (infinite time to normalize bilirubin) and were not censored before reaching the endpoint of interest. Results of these analysis will be compared with results of analysis excluding subjects who die or are transplanted. Time to reach a total bilirubin of 1.2 will also be compared using survival analysis methods. Analysis of this outcome will proceed as described for direct bilirubin.

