We will also describe individual profiles over time (i.e., 2 months before baseline or birth until end of follow-up period) for all subjects using graphical methods. Trends in liver function markers over time will be explored using generalized linear models in which correlations of observations within subjects will be accounted using a generalized equations or random effects approach. In these models we will hypothesize that for both groups biochemical levels increase for all tests with equal slope before treatment. After treatment, however, levels should be decreasing for patients in the Omegaven® group. We will perform these analyses including only subjects who did not die or undergo transplantation and including all subjects but assigning for subjects who died or underwent a transplant their worse possible outcome after they died or had the transplant. Using descriptive statistics, we will also explore the association between spikes in blood tests over time and predictors including transfusions of red blood cell products and blood stream infections.

Assessment of efficacy will be also based on comparison of means (or medians) of the mean and maximum modified PELD scores of each subject across all follow-up weeks. Adjustments of these comparisons for potential confounders will be based on linear regression models. Mean rates of infection will be compared using logrank and Cox proportional hazards models. Proportions of liver transplant, mortality, and red blood cell product transfusion events between the two groups will be compared via Fisher's exact test (or Chi-square tests, when appropriate). Adjustments for potential confounders will be considered using exact stratified analysis and logistic regression models.

Missing Values

Since data will be prospectively collected in the Omegaven® group, we anticipate that data will be nearly complete, particularly for the safety outcomes. In both groups, we will explore imputing any laboratory values that are missing up to two visits in the middle of the follow-up period using linear or non-linear interpolation, as appropriate. To interpolate direct and total bilirubin, we will primarily use the two closest observations, since bilirubin could be very different in points in time located further apart from the missing observation. We will compare conclusions of analyses based on imputed values with analyses based on the available information.

Potential Study Limitations

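### The infinite-time rule for death or transplant is worded to cover every log-rank and Cox analysis, including infection, for which the plan gives no other rule

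*Combined protocol and SAP*

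**What the plan says.** The rule stands in section 5c, Analysis of Efficacy, in the text on time to normalise direct bilirubin. Its scope is "For all survival analysis based on non-parametric or semi-parametric methods, we will attribute an infinite time to event", with infinite explained as "time to event larger than the largest follow-up time in the whole study population". It is triggered "for subjects who die or receive a liver transplant before bilirubin is normalized". The justification is that patients who die before normalising "have in fact the worse outcome (infinite time to normalize bilirubin) and were not censored before reaching the endpoint of interest". One sensitivity analysis is attached: "Results of these analysis will be compared with results of analysis excluding subjects who die or are transplanted". The method is carried over explicitly to one further endpoint, total bilirubin: "Analysis of this outcome will proceed as described for direct bilirubin".

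Later under the same heading comes the infection comparison: "Mean rates of infection will be compared using logrank and Cox proportional hazards models". That sentence does not refer back to the rule, does not say how death or transplant is handled, and does not define the event or the time origin.

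Elsewhere infection is treated as a rate over observed time. Section e (Definition of Primary and Secondary Outcomes/Endpoints) lists the "rate of blood stream infections (number of positive blood cultures/follow-up-time under PN after baseline", and the safety analysis in section 5c includes Poisson rates among its summaries.

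**The concern.** An infinite event time is the worst score only when the event is good. For bilirubin normalisation it does what the plan wants, because a child who dies never normalises. For infection it is the best score: a child who dies uninfected would be carried in the risk set as permanently infection-free. That is the reverse of the plan's evident aim, since its repeated-measures models give patients who die or are transplanted their worst possible value.

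The comparison at stake is hypothesis 2.3 (fewer infections on Omegaven). Unequal death rates are likely. Hypothesis 2.4 expects fewer transplants and hepatic deaths on Omegaven, whereas the sections on additional predictors and on limitations expect sicker patients in that group. The distortion could therefore run either way.

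A smaller issue touches the primary efficacy endpoint. Patients who die stay at risk beyond everyone's follow-up, while living patients leave at loss or at the data cut. If that censoring differs between groups, the dead carry unequal weight and the hazard ratio moves without any drug effect.

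**Working it through.** The documents give no event count, power or hazard ratio for any survival analysis (Tables 4 and 5 concern McNemar and Fisher tests), so there is no plan figure to reproduce.

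**Step 1: the text side by side.**
- Scope words: all non-parametric and semi-parametric survival analyses. Log-rank and Cox for infection fall within them.
- Trigger, rationale and position: all concern bilirubin normalisation.
- Infection denominator in section e: follow-up time under PN. A patient who has died contributes none, so an infinite time at risk contradicts it. Transplant is also a listed reason for withdrawal from the study.
- Other rule for death or transplant in the infection analysis: none found.

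**Step 2: why the estimate moves.** Let h be the infection hazard, equal in both groups, and d the death hazard. If uninfected deaths stay in the risk set, the apparent infection hazard at time t is h × A/(A + D), where A = exp(−(h+d)t) is the proportion alive and uninfected and D = [d/(h+d)] × (1 − A) is the proportion dead and uninfected.

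Assume a normalisation hazard of 0.15 per month. Death before normalising in 10% and 25% of patients then needs d = 0.15 × 0.10/0.90 = 0.0167 (Omegaven) and d = 0.15 × 0.25/0.75 = 0.05 (control). With h = 0.10, at 6 months, ignoring patients who leave after normalising:
- Control: A = exp(−0.90) = 0.407; D = 0.333 × 0.593 = 0.198; A/(A+D) = 0.673.
- Omegaven: A = exp(−0.70) = 0.497; D = 0.143 × 0.503 = 0.072; A/(A+D) = 0.874.
- Apparent hazard ratio at that moment: 0.874/0.673 = 1.30, although the true value is 1.

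**Step 3: averaged over follow-up.** Large-sample simulation with exponential times, infection hazard 0.1–0.2 per month, normalisation hazard 0.15 per month, and follow-up to death or 2 months after normalising (the window in section e). Only uninfected deaths are set to infinity; the true hazard ratio is 1.

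| Deaths before normalising, Omegaven vs control | Infinite time | Censored at death |
|---|---|---|
| 10% vs 25% | 1.17–1.23 | 1.00–1.01 |
| 10% vs 40% | 1.42–1.53 | 1.00 |
| 20% vs 20% | 1.00 | 1.00 |

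**Step 4: small samples.** A second simulation used 30 or 50 per group (30 is the largest size in the power tables, 50 the planned size of the contemporary control cohort). It assumed 12 months of follow-up, 12-month infection risk of 40% or 70%, and deaths of 5% vs 20%, 10% vs 30% or 10% vs 40%. The median hazard ratio was 1.09–1.24, with log-rank rejection of 5.8–13.6% at a nominal 5%. Censoring at death gave 0.99–1.01 and 4.5–5.9%.

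**Step 5: bilirubin.** Identical hazards in both groups (normalise/die 0.15/0.05 or 0.10/0.10 per month), with the infinite-time rule as written:

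| Assumed censoring | Hazard ratio (true value 1) |
|---|---|
| Omegaven accrual over 2 years, complete controls | 0.90–0.91 |
| Omegaven accrual over 5 years, complete controls | 0.96–0.97 |
| Omegaven accrual over 10–14 years, complete controls | 0.98–0.99 |
| Control loss 2–5% per month | 1.03–1.11 |
| Control loss 0.5–1% per month | 1.01–1.02 |

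Keeping the dead at risk only to the date on which they would otherwise have been censored gives 0.99–1.01.

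**The case against.** The strongest reply is that the rule was plainly written for bilirubin. Its trigger is death or transplant before bilirubin normalises, its rationale speaks of time to normalise bilirubin, and its only explicit extension is to total bilirubin. The infection sentence speaks of mean rates and names no time-to-first-infection endpoint. All of this stands, and a bilirubin-only scope is probably what was intended. It does not close the gap: if the rule is not meant for infection, the log-rank and Cox analysis of infection has no rule for death or transplant. Either reading needs the same correction.

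Three stronger readings are tempting, and the documents do not support them.
- A reader might infer that every death counts as infection-free. Even taken literally, the rule covers only deaths and transplants before normalisation.
- A reader might let the infinite time replace infections already recorded before death, which gives hazard ratios of about 1.45–2.2. Nothing in the plan suggests overwriting observed events, so those figures should not be used.
- A reader might infer that the wording manufactures an infection benefit for Omegaven. With more deaths among controls, it works against Omegaven; it would favour Omegaven only if deaths before normalisation were commoner there.

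On bilirubin, the reply is that the larger shifts need short accrual or heavy loss. The document is dated 2021 and mentions an approval to bill for the drug in March 2007, so accrual over some 14 years is plausible. A control loss of 5% per month means 1 − exp(−0.60) = 45% per year, and the source cohort excluded incomplete records. That reply largely stands and makes this the minor part. The planned sensitivity analysis does not remove the shift, because excluding patients who later die or are transplanted conditions on a later outcome.

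**Conclusion.** The point holds as a fault of scope and omission in a secondary analysis. The infinite-time rule is worded more broadly than its rationale allows, and the infection log-rank/Cox comparison has no other handling of death or transplant. Followed literally, with deaths before normalising at 10% on Omegaven and 25–40% in controls, a true infection hazard ratio of 1 would be estimated at about 1.2–1.5. Equal death rates give no bias. The death, infection and normalisation rates are all assumptions, so this range shows the mechanism and does not predict the trial's result.

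For bilirubin the effect on the primary hazard ratio is real but small: about 1–3% under long accrual or light loss, and up to about 10% under short accrual or heavy control loss, again on assumed rates. It is modest beside the historical-control confounding that the plan itself names as its main limitation. Both parts are worth correcting because the changes remove bias at almost no cost.

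**What to change.** In section 5c, Analysis of Efficacy:

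1. Limit the infinite-time rule to the two normalisation endpoints, direct bilirubin and total bilirubin.
2. For infection, define the event (first infection or all infections) and the time origin, and end time at risk at death or transplant. Analyse it as a cause-specific hazard with censoring at those events, or as a rate over person-time under PN, which would match section e.
3. For the bilirubin endpoints, keep patients who die or are transplanted at risk only to the date on which their follow-up would otherwise have ended. Alternatively, use cumulative incidence with a Fine-Gray model and group-specific censoring weights.

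The cost is a few sentences in the plan and standard software. Item 3 also needs a potential end-of-follow-up date for each patient who dies or is transplanted, such as the data cut, or the Fine-Gray weights where that date is not known.

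### The only comparison planned for the infinite-time rule deletes patients who die or are transplanted; when those risks differ between groups it cannot separate faster bilirubin normalization from fewer deaths and transplants

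*Combined protocol and SAP*

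**What the plan says.** Section 5c, Analysis of Efficacy of Omegaven, states that the primary efficacy outcome "will be based on the time from baseline to normalization of bilirubin level". Crude comparisons "will be based on Kaplan-Meier curves and log-rank tests", and Cox models give adjusted hazard ratios.

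For death and transplant the plan has one rule and one comparison:

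- **Rule.** "we will attribute an infinite time to event" "for subjects who die or receive a liver transplant before bilirubin is normalized". The stated reason is that death before normalization is the worst outcome and should not be treated as censoring.
- **Comparison.** "Results of these analysis will be compared with results of analysis excluding subjects who die or are transplanted". Unlike the rule, this wording is not limited to events before normalization.

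The exploratory trend models for liver markers are to be run twice: once "including only subjects who did not die or undergo transplantation", and once on all subjects with the worst possible value assigned after death or transplant.

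Death and transplant are also compared as proportions, by Fisher's exact or chi-square tests, with stratified or logistic adjustment considered. No analysis censors at death or transplant, and no cumulative incidence curve is planned.

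**The concern.** Whether a patient will die or be transplanted is unknown at baseline. Deleting those patients conditions on a later outcome and throws away the months they spent under observation without normalizing. In a group with many deaths, the patients who remain look as if they normalize quickly, because the slow ones had more time to die and be removed.

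The infinite-time analysis moves the other way. Patients who die stay in the risk set as never normalizing, so a group with more deaths looks slower. This is a defensible composite-type choice, but its hazard ratio mixes normalization with death and transplant.

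Hypothesis 2.1 says Omegaven patients will normalize faster, and hypothesis 2.4 says they will have fewer transplants and hepatic deaths. A reader of the primary result will want to know which of the two produced it. Two analyses that both mix the events, in opposite directions, cannot answer that.

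**Working it through.** **No plan figure to reproduce.** The only power figures (section 5d, Tables 4 and 5) concern safety. The documents give no rate of normalization, death or transplant, so every hazard below is an assumption.

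**Model.** Two independent constant monthly hazards: a for normalization and b for death/transplant. T is Omegaven, C is control, and follow-up is 24 months.

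**What deletion estimates.** Among patients who normalize before death or transplant, the time to normalization is exponential with rate a + b, not a. With complete follow-up the exclusion hazard ratio therefore tends to

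(aT + bT) / (aC + bC), whereas the ratio of normalization rates is aT / aC.

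**No effect on normalization (aT = aC = 0.08).**

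- Hazards bT = 0.01, bC = 0.04: limit 0.09 / 0.12 = 0.75.
- Reversed: 0.12 / 0.09 = 1.33.
- Equal, 0.02 each: 0.10 / 0.10 = 1.00.

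The share who die or are transplanted first by 24 months is b/(a+b) × (1 − exp(−24(a+b))):

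- b = 0.01: 0.111 × (1 − exp(−2.16)) = 0.098, about 10%.
- b = 0.04: 0.333 × (1 − exp(−2.88)) = 0.315, about 31%.

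**Simulation with censoring at 24 months.** Cox hazard ratios, Omegaven versus control, 200,000 per group. Exclusion here deletes patients whose death or transplant comes before normalization.

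| True ratio | bT, bC | Death/transplant T, C | Infinite time | Exclusion | Cause-specific |
|---|---|---|---|---|---|
| 1.0 | 0.01, 0.04 | 10%, 31% | 1.39 | 0.79 | 1.00 |
| 1.0 | 0.04, 0.01 | 31%, 10% | 0.72 | 1.27 | 1.00 |
| 1.0 | 0.02, 0.02 | 18%, 18% | 1.00 | 1.00 | 1.00 |
| 2.0 | 0.01, 0.04 | 6%, 31% | 2.44 | 1.52 | 2.01 |
| 2.0 | 0.04, 0.01 | 20%, 10% | 1.29 | 2.25 | 1.99 |
| 2.0 | 0.02, 0.02 | 11%, 18% | 1.78 | 1.88 | 2.01 |
| 1.4 | 0.01, 0.05 | 8%, 37% | 2.01 | 1.01 | 1.40 |

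In the first two rows the planned pair falls on opposite sides of 1 although normalization is unaffected. In the last row a true 40% gain disappears under exclusion.

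**Small samples.** With 30 per group (the largest size in Tables 4 and 5) and an assumed two-sided 5% log-rank test, rejection in row 1 is 19% (infinite time), 13% (exclusion) and 5% (cause-specific). In row 4 it is 86%, 26% and 64%.

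**Relaxing independence.** Censoring returns the input ratio above because the hazards were made independent. Suppose instead that a shared log-normal severity (assumed SD 0.7 to 1.0) slows normalization and raises death/transplant, with death/transplant of about 36–38% in one group and 16–19% in the other. With no effect on normalization:

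| Higher death/transplant in | Infinite time | Exclusion | Cause-specific |
|---|---|---|---|
| Controls | 1.29 to 1.26 | 0.72 to 0.71 | 0.93 to 0.91 |
| Omegaven | 0.77 to 0.78 | 1.37 | 1.06 to 1.08 |

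The cause-specific estimate is no longer exact, but it stays closest to 1.

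**The case against.** **The primary analysis is sound on its own terms.** Treating death as the worst outcome is deliberate and explained, and it keeps every patient. That stands. A reader might infer that the cause-specific ratio should become the primary analysis because hypothesis 2.1 says faster. The documents do not require that reading. The two ratios answer different questions, and the cause-specific one explains the primary result without validating it.

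**The exclusion analysis is not worthless.** A reader might infer that it tells us nothing. With equal death/transplant hazards it keeps the null and only shrinks a real effect (1.88 against 2.01). The difficulty is that the plan expects unequal hazards.

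**The direction is not fixed.** A reader might infer that the plan favours Omegaven. Hypothesis 2.4 points that way for the infinite-time analysis. But Additional Predictors of Interest and Potential Study Limitations both expect Omegaven patients to have more severe disease, which could reverse it.

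**The literal exclusion wording may behave differently.** It also deletes patients who normalized and later died or were transplanted. If death/transplant were independent of normalization, unchanged by it, and observed for a period that does not depend on recovery, that deletion would be unrelated to normalization time and would not bias the ratio. The plan does not offer those conditions. Its own rationale links bilirubin to liver failure. For Omegaven patients, death and transplant are collected during treatment, which ends when they are off PN; for controls, over the whole available dataset.

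**Death and transplant are visible elsewhere.** The comparison of proportions would show an imbalance, and the trend models are not restricted to survivors, since an all-subjects version is also planned. Both points are fair. Neither shows how much of the primary hazard ratio comes from normalization.

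**Conclusion.** The point holds for the comparison analysis, not for the primary. Excluding patients who die or are transplanted conditions on a post-baseline outcome, and nothing else in the plan separates the two events over time. When their hazards differ between groups, neither agreement nor disagreement with the primary result can be interpreted. Under the assumed hazards, with no effect on normalization and about 10% against 31% death/transplant, the distortion is about 0.8 in one direction and 1.3 in the other; with equal hazards it vanishes.

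These sizes depend on assumed rates, constant hazards, 24 months of follow-up and deletion of events before normalization. The cause-specific model is exact only when the hazards are independent; with shared severity it was about 0.9 or 1.1 when the truth was 1.0. The study is non-randomized, is not powered for efficacy and seeks preliminary evidence, so this should be corrected but does not undermine the primary analysis.

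**What to change.** In section 5c:

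1. Keep the infinite-time analysis as primary.
2. Replace the exclusion analysis with a cause-specific Cox model that censors at death or transplant before normalization, using the same baseline adjustment.
3. Report beside it cumulative incidence curves for normalization and for death/transplant, by group.
4. State that the cause-specific ratio is a different estimand, reported to explain the primary result, and that it is only approximately unbiased if unmeasured severity affects both events.
5. In the exploratory trend models, replace the survivors-only version with one using all values observed up to death or transplant, beside the planned all-subjects worst-outcome version.

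This needs only a change of wording, with the same data and standard software. The downside is one more estimand to interpret.
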